## SYNOPSIS

Title: DAICY trial – Dual vs. Single-Antibiotic Impregnated Cement in Hemiarthroplasty for Femoral Neck Fracture: A Register-based cluster-randomized cross-over controlled trial

Rational for conducting the study: Periprosthetic joint infection (PJI) is the most feared complication following prosthetic replacement of the hip joint and is associated with increased mortality, morbidity and economic burden. The aim of the trial is to investigate whether the risk of periprosthetic joint infection after treatment with hemiarthroplasty performed due to femoral neck fracture is reduced after the use of dual-impregnated antibiotic loaded cement. Our *primary outcome variable* is the incidence of periprosthetic joint infection within one year after the index procedure. Secondary outcome variables include the occurrence of re-operations for any reason, bacteriology, antibiotic treatment, mortality and health care costs.

Study design: Register-based, cluster randomized controlled trial

Study population: Patients aged ≥60 years

## Number of patients: 7,000

Inclusion criteria:

- Age ≥60 years
- Diagnosis: displaced femoral neck fracture type AO 31-B2 or B3/Garden type 3 or 4
- Eligible for hemiarthroplasty according to local guidelines and routines

#### **Exclusion criteria:**

- Previous inclusion of contralateral hip in the present study
- Pathological or stress fracture of the femoral neck, or fracture adjacent to a previous ipsilateral hip implant
- Unavailability of both interventions for a study participant (e.g., sensitivity to any of the components in the bone cement)
- Patients that have actively marked their hospital charts with an added privacy notice

#### Primary outcome variable:

The primary outcome will be the occurrence of periprosthetic joint infection of the index joint within one year.

Trial period: Jan 1st 2022 - Jan 31st 2027

	DAICY		
Clinical Study Protocol	Version No:	1.0	
	Date:	2021-11-17	

## LIST OF ABBREVIATIONS

Abbreviation	Explanation
ASA	American Society of Anaesthesiologists
DIAC	Dual-Impregnated Antibiotic Cement
FNF	Femoral Neck Fracture
HA	Hip Hemiarthroplasty
ICD	International Classification of Diseases
PJI	Periprosthetic Joint Infection
NPR	National Patient Register
RCT	Randomized Controlled Trial
SAR	Swedish Arthroplasty Register
SDR	Swedish Drug Registry
SFR	Swedish Fracture Register

DAICY	
Version No:	1.0
Date:	2021-11-17

## 1. INTRODUCTION

#### 1.1. Background

In Sweden, *hip fractures* annually affect close to 20,000 elderlies, often frail patients. Although the incidence of this injury seems to be stabilizing or even slightly declining, hip fractures cause an annual economic burden of no less than 800 million  $\in$  in Sweden alone and the costs are increasing (1, 2).

Femoral neck fractures (FNFs) are mainly a fragility fracture in the elderly and frail, predominantly affecting women after menopause but reports have indicated an increased incidence in elderly men (3). The average age of patients suffering a hip fracture has been increasing over the last decade and is around 80 years with an exponential increase of incidence with age (4). The lifetime risk of hip fracture in Sweden is 20% for women and 11% in men (5). A hip fracture is related to a doubled risk of death during the first year after fracture in comparison to age-matched controls (6).

FNFs are classified according to the degree of fracture displacement and the most widely used is the Garden classification. As displacement increases, the risk of disruption of the blood supply to the femoral head increases. Displaced fractures represent two thirds of the FNFs. With a disrupted vascular supply, the risk for healing disturbances, complications and reoperations increases when treated with internal fixation with screws or pins. For displaced fractures in elderly patients treated with internal fixation, failure rates of 35-50% have been reported in the literature (7). The most frequent complications are avascular necrosis and pseudarthrosis due to disrupted vascular supply of the femoral head and mechanical failure due to inadequate fixation (8). Long-term follow-up studies have emphasized the superiority of replacing the joint by hip arthroplasty in comparison to internal fixation in regard to hip function (9-11). Hip arthroplasty with either a total or hemiarthroplasty is a reliable option due to its ability to restore hip function and reduce the need for secondary surgery after an FNF (12). In hip arthroplasty implants are fixed to the bone with or without the use of bone cement (polymethyl methacrylate). Uncemented fixation in FNF patients has been linked to an increased risk for periprosthetic femoral fractures (13). In Sweden cemented hip arthroplasties are most frequently used and are regarded as the gold standard for FNF patients.

Bone cement or polymethyl methacrylate (PMMA) is widely used for implant fixation in orthopaedic procedures. PMMA acts as a void-filler that creates a tight space which holds the implant against the bone and acts as a 'grout'. Bone cements have no adhesive properties and rely instead on close mechanical interlock between the irregular bone surface and the prosthesis. PMMA is an acrylic polymer that is formed by mixing 2 sterile components, a liquid methyl methacrylate monomer and a powdered methyl methacrylate-styrene polymer. When mixed the liquid monomer polymerizes around the pre-polymerized powder particles to form hardened PMMA. An exothermic reaction generate heat in the process which reaches temperatures of around 82–86 °C in the body. In order to make the cement visible on radiographs, a contrast agent is added (zirconium dioxide or bariumsulphate).

Bone cement has proven useful as carrier of specific active substances, e.g., antibiotics added to the powder component. Antibiotics are delivered directly to the surgical site which in turn give a high

	DAICY	
Clinical Study Protocol	Version No:	1.0
	Date:	2021-11-17

concentration and low systemic concentration well below the clinical routine dosages for systemic single injections. Various antibiotics have been successfully mixed and used with bone cements like gentamycin, clindamycin etc. Compared to intramuscular administration, systemic concentration levels of gentamycin are low with bone cement, usual maximum concentrations below 1  $\mu$ g/ml (<10%) without any detectable systemic levels after 7 days. In Sweden, antibiotic loaded cement is routinely used and represents the standard of care in cemented primary total hip arthroplasty, always in combination with systemic prophylaxis to reduce the risk for revision surgery due to periprosthetic joint infection (PJI) (14-17). The type of antibiotic impregnated bone cement varies between regions, countries and type of surgical procedure performed.

In Sweden, the most commonly used cement is the low dose ( $\leq 2$  g of antibiotic powder per 40 g cement) impregnated cement (Gentamycin). For revision procedures, a higher dose of gentamycin in combination with either vancomycin or clindamycin is often used and labelled dual-impregnated antibiotic cement (DIAC). For patients at risk for sustaining a PJI, i.e., hip fracture patients, some hospitals routinely use dual-impregnated antibiotic cement for hip arthroplasty procedures.

Surgical site infection (SSI) remains a severe complication linked to increased mortality, prolonged hospitalization, revision surgery, long-term treatment with antibiotics, dramatically increased costs and a strenuous rehabilitation (18). SSI is the third most commonly occurring healthcare-associated infection, accounting for 16% of reported infections (18). Rates of infection up to 7.3% for hemiarthroplasty have been reported (19). Parenteral antibiotics in elective primary total hip arthroplasty for osteoarthritis, have been shown to reduce SSI and antibiotic loaded cement, combined with systemic antibiotics is considered to be the most effective prophylaxis against infection (15, 16). The potential of developing resistance among infecting organisms by using local antibiotics in general and especially DIAC has been under discussion but the clinical evidence remains sparse (20, 21).

In a recent randomized study from England, the rate of infection following hemiarthroplasty for FNF was reduced from 3.5% with conventional single-impregnated antibiotic-loaded cement to 1.1% by using high-dose DIAC (22). Observational studies have indicated similar reduction in PJI (20, 23). At present there is one ongoing large scale clinical (White 8) trial to further entangle the potential effect of DIAC in the United Kingdom (24). The aforementioned study has a shorter follow-up and the occurrence of multi- and pan-resistant bacteria is higher in the United Kingdom. The differences motivate a Scandinavian multicentre trial, for better external validity. The chosen outcomes in the above mentioned and the present trial will enable us for a future comparison of the obtained results.

#### 1.2. Rationale for conducting this study

Dual-impregnated antibiotic loaded cement is promising in lowering the incidence of periprosthetic joint infection, however there is a need for large, sufficiently powered randomized controlled trials in a Scandinavian setting. In this prospective register-based cluster randomized cross-over study, the aim of is to compare standard low dose antibiotic impregnated cement and DIAC in patients above 60 years old with a FNF amenable for HA according to local guidelines. The primary outcome will be reoperations due to infection within 1 year.

DAICY	
Version No:	1.0
Date:	2021-11-17

## 2. STUDY OBJECTIVES AND ENDPOINTS

#### 2.1. Primary objective

1) The primary objective is to assess whether DIAC reduces the risk of PJI in patients with a femoral neck fracture treated with a HA by 50% within one year.

## 2.2. Secondary objective(s)

The secondary objective(s) of this study are to evaluate whether there is a difference between the intervention and control group in:

[figure not shown]
- 1) Antibiotic prescription obtained from the Swedish Drug register at 120 days and 1-year post-surgery.
- Resistance patterns of infections; all infections identified in the primary endpoint will be assessed for antibiotic resistance profiles. Identified in the NPR or SAR and obtained by assessing the medical files.
- Mortality obtained from the Swedish Fracture Registry (SFR) within 90 days and 1-year post-surgery.
- 4) Resource use; cost data will be obtained from national databases or will be estimated in consultation with the hospital finance department at 120 days and 1-year post-surgery.

## 3. STUDY DESIGN AND PROCEDURES

#### 3.1. Overall study design and flow chart

The proposed study is designed as a prospective register-based cluster randomized cross-over study design. The study will be pragmatic, with broad eligibility criteria, participant inclusion by treating department (site), and great freedom for surgeons to choose between different implant brands, surgical approaches and post-operative regimes.

Two thirds of Swedish patients 60 years and above with a displaced femoral neck fracture receive a cemented HA. 2230 procedures were registered in the SFR during 2019 and were eligible for inclusion in the present study.

## 3.2. Rationale for study design

The prospective register-based cluster randomized cross-over study design enables us to perform a national multicenter registry-based study without any additional follow-up visits. In this elderly population with a high prevalence of cognitive impairment, the main advantage is the possibility to recruit a large sample size without burden the patients with additional follow-up visits. The study population consists of an elderly and fragile group of patients, with a high burden of comorbidities, with the need of acute surgery with a HA after sustaining an FNF. This acute situation provides challenges to scientific evaluation and feasibility of participation in large multicenter clinical trials. The cluster randomized design is fundamental to the feasibility of recruitment and evaluation in this fragile group of patients.

The Swedish personal identity number allows the investigator to link registers on an individual level. Data on fracture classification, age, sex, type of trauma, time of diagnosis with radiography, time of surgical treatment will be collected in the SFR and the randomization will be performed within the SFR registry-platform. Further variables will be retrieved by cross-linking with the SAR with data on manufacturer and type of components (uni- or bipolar), cement type and any revision surgery performed. Data on reoperations are registered in the NPR. Mortality data is automatically available within the SFR and SAR, from the Swedish Tax Agency.

DAICY	
Version No:	1.0
Date:	2021-11-17

## 3.3. Study visits

There will be no formal clinical follow-up visits in addition to the local clinical routines. Data on reoperations and mortality is registered in the SFR, NPR and SAR.

## 4. STUDY POPULATION

#### 4.1. Inclusion criteria

- Age ≥60 years
- Diagnosis: displaced femoral neck fracture type AO 31-B2 or B3/Garden type 3 or 4
- Eligible for HA according to local guidelines and routines

#### 4.2. Exclusion criteria

- · Previous inclusion of contralateral hip in the present study
- Pathological or stress fracture of the femoral neck, or fracture adjacent to a previous ipsilateral hip implant
- Unavailability of both interventions for a study participant (e.g., sensitivity to any of the components in the bone cement)
- Patients that have actively marked their hospital charts with an added privacy notice

#### 4.3. Subject enrolment and randomization

In the first step of the study, the orthopedic departments included are randomized to start with either the control or intervention treatment. After the first period of 2 years is completed, the study site will change to use the other treatment for the patients included in the following period of 2 years. At each department, information regarding the study is made available on the official web page, the orthopedic ward and the outpatient department. All patients admitted and fulfilling the inclusion criteria and registered in the SFR or SAR will be included. After the index surgery, procedural details and patient characteristics will be collected within the SAR. Procedural details include type and brand of implant, type of components (uni- or bipolar head), type of cement (intervention: DIAC or control: Single-impregnated antibiotic-laden bone cement), surgical approach and type of antibiotic prophylaxis. Patient characteristics registered in the SAR include indication for surgery, age, sex, American Society of Anesthesiologists (ASA) grade and body mass index (BMI). Data on revision surgery performed and on reoperations are registered in the SAR. Data on reoperations are also registered in the NPR. Mortality data are automatically available within the SFR and SAR from the SDR.

#### 4.4. Discontinuation and withdrawal of subjects

Subjects are free decline registration or to discontinue their participation in the SFR or SAR at any time without prejudice to further treatment. Already collected study data for these patients will be kept in the study database, however new data, including data from registries will not be added. Patients prematurely withdrawn from the study will not be replaced.

	DAICY	
Clinical Study Protocol	Version No:	1.0
	Date:	2021-11-17

## 4.4.1. Premature termination of the study

The study group may decide to stop the trial or part of the trial at any time. Furthermore, the investigator should promptly inform the Ethics Committee and provide a detailed written explanation.

## 5. STUDY TREATMENTS

## 5.1. Identity of investigational implants

Group 1 (control): Cemented hemiarthroplasty with low dose single antibiotic cement Replacement of the femoral head and neck with choice of femoral head and stem. Cement used will be Heraeus Palacos R+G cement (Hanau, Germany) or Zimmer/Biomet Optipac cement – contains gentamicin 0.5 grams per 40 grams mix of cement.

Group 2 (exposed): Cemented hemiarthroplasty with high dose dual-impregnated antibiotic cement Replacement of the femoral head and neck with choice of femoral head and stem. Cement used will be Heraeus Copal G+C cement (Hanau, Germany) – contains gentamicin 1 g and clindamycin 1 g per 40 gram mix of cement.

#### 5.2. Blinding

There will no blinding of the bone cement for the surgeon.

#### 5.3. Randomization

All participating departments will be randomized in a 1:1 ratio to either the sequence dual impregnated antibiotic cement (intervention) period followed by standard cement (control) period, or the sequence control period followed by intervention period. All participating departments will be randomized once, using a single permuted block of size equal to the number of clusters (or the number of clusters plus one if the number of clusters is odd). We do not expect to enroll further clusters after trial start, but in that event, new clusters will be randomized to either treatment sequence using 1:1 simple randomization, to ensure that the decision to enter the trial is not affected by knowledge of treatment sequence allocation.

#### 5.4. Concomitant medication

Patient will receive their ordinary medications and the standard pre- and postoperative treatment at each participating center including standard preoperative antibiotic prophylaxis.

## 6. STUDY MEASUREMENTS AND VARIABLES

#### 6.1. Primary outcome variable

Periprosthetic joint infection of the index joint within one year

The definition of PJI will be that the treating physicians defined presence of a PJI and started treatment (re-operation, or suppressive antibiotics, or combinations thereof). The investigators will use the SFR, NPR, SAR and the SDR to identify potential PJI by the registration of any of the International Classification of Diseases (ICD; version 10) codes or NOMESCO codes indicative of

	DAICY	
Clinical Study Protocol	Version No:	1.0
	Date:	2021-11-17

this complication (see Appendix 1). In cases when these codes are present a review of the medical records will be performed to identify patients.

The hazard of infection in the intervention compared to the control group will be assessed by fitting adjusted Cox proportional hazards models.

The review of medical records will capture any re-operation records for surgery related to the index hip fracture, details of antibiotics prescribed, microbiology reports if samples of the suspected infected tissues around the hip were sent for analysis.

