#### Antibiotic suppression

Antibiotic prescription information will be obtained from the Swedish Drug Register at 120 days and 1-year post-surgery.

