#### 7.1. Statistical analysis

Generally, all statistical analyses will account for the cluster-randomized crossover design to ensure correct type I error rates and confidence intervals (CIs). Analyses will be performed using the intention-to-treat principle including all eligible patients with available follow-up data within a study site according to allocated treatment for the study site. The threshold of statistical significance will be set at a 2-sided p-value of 0.05.

As primary analysis, the difference in risk of PJI after the intervention treatment compared to the control group will be estimated using linear regression for aggregated cluster-period data, with proportion of events within a cluster period as dependent variable and treatment, cluster, period

	DAICY	
Clinical Study Protocol	Version No:	1.0
	Date:	2021-11-17

and proportion of females within the cluster period as independent variables. Estimated difference in risk with 95% confidence interval and 2-sided p-value will be presented.

With the registry-based follow-up we assume that follow-up will be complete and the quality of data adequate with confirmation of data in an individual medical charts review. In the rare case that a patient has incomplete follow-up and a value for primary outcome is missing the patient will be excluded from analysis. Death before PJI will be handled as no PJI.

Secondary event outcomes will be analyzed and described in the same way as for the primary outcome.

Supplementary and sensitivity analyses will be performed for all event endpoints. An analysis of the primary outcome including all ITT patients will be performed using multiple imputation for individual outcomes based on individual patient characteristics, details to be described in the Statistical Analysis Plan. Sensitivity analyses to investigate the impact of handling death as non-event, in addition to analyzing death as a secondary outcome, will include analyses of the composite of PJI and death. As a sensitivity analysis for the asymptotic approximation in the linear model, a 2-sided p-value for no difference in proportion will be obtained by Monte Carlo randomization inference based on the likelihood ratio.

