# Appendix 1. ICD codes for primary and secondary outcomes.

Endpoint	ICD	NOMESCO
Periprosthetic joint infection	M00.0, M00.0F, M00.1, M00.2, M00.2F, M00.8, M00.8F, M00.9, M00.9F, M86.0F, M86.1F, M86.6, M86.6F, T81.4, T84.5, T84.5F, T84.5X, T84.7, T84.7F	NFSx, NFA12, TNF05, TNF10
Any reoperation		Any of the codes above, and: NFA00-22, NFA31-32, NFCx, NFF01-12, NFL09- 19, NFL39-49, NFL69-99, NFM09-29, NFM49, NFM79-99, NFTx, NFWx
Endpoint	ATC	Minimum number of tablets
Drug prescription	J01XX08: 56 st J01XA02: 28 st J01XA01: 56 st J04AB02: 28 st J01XC01: 168 st J01XC01: 168 st J01CF05: 84 st J01FF01: 56 st J01CA04: 84 st P01AB01: 84 st J01AB01: 84 st J01MA02: 56 st J01MA12: 28 st J01MA14: 28 st J01DE02: 168 st J01DB05: 56 st J01DD04: 28 st J01DD04: 28 st J01FA06: 56 st J01FA15: 56 st J01FA15: 56 st J01FA15: 56 st	56 st 28 st 56 st 28 st 28 st 168 st 84 st 56 st 5

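### Section 6.1 counts PJI treated with antibiotics alone and names the drug register as a source, but opens charts only on ICD or NOMESCO codes

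*Protocol*

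**What the plan says.** Section 6.1 of the protocol requires that the treating physicians judged a PJI to be present and "started treatment (re-operation, or suppressive antibiotics, or combinations thereof". Antibiotics without surgery are therefore enough.

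On finding cases, the same section says: "The investigators will use the SFR, NPR, SAR and the SDR to identify potential PJI by the registration of any of the" ICD-10 or NOMESCO codes in Appendix 1. It continues: "In cases when these codes are present a review of the medical records will be performed to identify patients". No other route to chart review is described.

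The data-collection table in Section 7.2 ticks the drug registry as a source for PJI, and separately for antibiotic suppression.

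The PJI row of Appendix 1 contains procedure codes and diagnosis codes, among them "T81.4, T84.5, T84.5F, T84.5X, T84.7, T84.7F". A further row, headed "Drug prescription", lists ATC codes with a column "Minimum number of tablets". Section 6.2 uses the drug register for a secondary outcome: "Antibiotic prescription information will be obtained from the Swedish Drug Register at 120 days and 1-year post-surgery".

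On completeness, Section 7.1 says: "we assume that follow-up will be complete and the quality of data adequate with confirmation of data in an individual medical charts review".

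**The concern.** The definition and the case-finding rule do not cover the same patients. The rule runs on ICD and NOMESCO codes, whereas the protocol uses the drug register for prescriptions, which Appendix 1 classifies by ATC code. The register is thus named as a source for PJI but has no stated way to supply a case. A patient whose PJI was treated with antibiotics alone, and who has no listed diagnosis code, meets the definition but not the trigger.

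Such a patient would not look like missing data. No code means no review, and the natural reading is that the outcome is then taken as no PJI. The protocol does not say this in words; it is an inference. If it is right, the planned sensitivity analyses do not reach the problem. Multiple imputation addresses missing outcomes, the composite with death addresses death, and randomization inference addresses the approximation in the linear model.

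The primary estimate is an absolute risk difference, so under-capture shrinks it even when equal in both arms. There is also a risk of late choice: if the trigger is settled only when the linked data are at hand, the decision could be influenced by what those data show.

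**Working it through.** **The passages side by side**

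| Element | What the protocol provides | Covers antibiotic-only PJI without a listed code? |
|---|---|---|
| Definition (6.1) | Physician-defined PJI, treated by surgery, antibiotics or both | Yes |
| Sources (6.1; table in 7.2) | SFR, NPR, SAR and SDR | Implied by naming the SDR |
| Trigger for chart review (6.1) | Listed ICD or NOMESCO codes | No |
| PJI row (Appendix 1) | ICD and NOMESCO codes | No |
| ATC list (Appendix 1) | Separate endpoint, no link to review | Not stated |
| Data linkage (7.3) | SFR, SAR and SDR merged, then ICD and NOMESCO codes from the NPR | No ATC screening step |

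The gap is confined to uncoded cases. The PJI row includes diagnosis codes such as T84.5, so a coded case reaches review whatever the treatment.

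**Reproducing the stated power**

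Inputs from the protocol's sample size section: 15 hospitals with the listed yearly volumes, two periods of two years, risks of 3% and 1.5%, two-sided 0.05, and three pairs of correlations. The volumes sum to 1,747 a year, and 1,747 × 4 = 6,988, against the stated 7,000.

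Data came from the protocol's logit model with normal cluster and cluster-period effects. The correlations were placed on the latent scale. The larger value ρ was taken as the same-period correlation and the smaller as the between-period correlation:

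- total random variance = ρ(π²/3)/(1 − ρ)
- cluster share = smaller/larger correlation = 0.8 in all three scenarios
- total variance = 0.033, 0.173 and 0.366 for ρ = 0.01, 0.05 and 0.1

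Intercepts were set so that the marginal risks are 3% and 1.5%. The analysis was an unweighted linear regression of cluster-period proportions on treatment, cluster and period, with a t-test on 13 degrees of freedom. With 10,000 data sets per scenario, power was 90.8%, 86.2% and 78.8%, against the stated 90%, 86% and 80%. The stated power is reproduced.

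**Illustration of missed cases**

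The protocol gives no share f of PJI that is antibiotic-only and uncoded, so f is an assumption, equal in both arms. Observed risks are 3%(1 − f) and 1.5%(1 − f). Their difference is 1.5(1 − f) points and their ratio stays at 0.5.

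| f | Risks, % | Difference, points | Power, % (small / medium / large correlation) | Loss, points |
|---|---|---|---|---|
| 0% | 3.00 vs 1.50 | 1.50 | 90.8 / 86.2 / 78.8 | – |
| 5% | 2.85 vs 1.425 | 1.43 | 89.3 / 85.6 / 77.7 | 1.5 / 0.6 / 1.1 |
| 10% | 2.70 vs 1.35 | 1.35 | 87.8 / 83.0 / 76.0 | 3.0 / 3.2 / 2.8 |
| 20% | 2.40 vs 1.20 | 1.20 | 83.3 / 78.5 / 72.5 | 7.5 / 7.7 / 6.3 |

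Simulation error per power figure is at most about √(0.79 × 0.21/10,000) = 0.4 points, so the losses at 5% are barely distinguishable from zero.

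These runs omit the proportion of females, which the planned model includes. A size-weighted variant with that covariate (4,000 runs) gave losses of 2.7 to 3.6 points at 10% and 4.5 to 5.6 points at 20%.

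**The case against.** The strongest reply is that a drug-based screen was plainly meant. Section 6.1 names the SDR for finding potential PJI, the table in Section 7.2 ticks it for PJI as well as for antibiotic suppression, and Section 6.1 points to an appendix that holds ATC thresholds. A literal reading leaves the first two statements without function. This stands as evidence of probable intent, but it does not supply the rule. The ATC row fits the secondary antibiotic outcome equally well. The analysis plan may contain a screening algorithm, but the protocol states the trigger itself and states it too narrowly.

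The size is open to challenge, and that also stands. The 5–20% range has no source in the protocol. The 3% control risk is described as resting on observed Swedish frequency and as conservative. If it already reflects incomplete case finding, discounting it again counts the loss twice. Equal under-capture leaves the relative risk at 0.5, and the primary objective is framed as a 50% reduction.

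A reader might infer that the comparison is biased, because surgeons are not blinded to the cement. The document does not support that. Nothing in it suggests that coding or the choice between surgery and antibiotics differs by cement. A difference in treatment choice would matter here only if the cases were also uncoded, and the direction would be unknown. The planned comparison of antibiotic prescriptions between arms could expose an imbalance, although it would not reclassify a case.

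**Conclusion.** The inconsistency is real and concerns ascertainment of the primary outcome. The definition and the named sources include PJI treated with antibiotics alone, but the written trigger for chart review does not use the drug register's prescription data. Followed literally, antibiotic-only PJI without a listed code is not reviewed.

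Two stronger readings are tempting and should not be drawn. One is that all antibiotic-only PJI is lost: coded cases are caught. The other is that the trial is shown to be underpowered: the stated power is reproduced, and the loss depends wholly on an unknown share. With equal under-capture it is negligible at 5%, about 3 percentage points of power at 10%, and 6–8 at 20% in the model that reproduces the stated figures. It matters most under large correlations, where the plan has 80% power and little to spare.

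The point should be corrected because the ambiguity affects who counts as a primary event and is easily removed before the outcome data are seen.

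**What to change.** In Section 6.1, state that medical records are reviewed for every participant who, within one year of surgery, has a listed ICD or NOMESCO code or a dispensing in the SDR that meets an ATC threshold in Appendix 1. In Appendix 1, list those thresholds under the PJI endpoint as well as under the existing drug-prescription endpoint.

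This takes one sentence and one appendix row, and the SDR data are already to be linked for all participants. The cost is extra chart review, because some long antibiotic courses are given for other reasons. Review confirms or rejects each candidate, so a wider trigger does not by itself add false events. If a drug-based trigger is not intended, Section 6.1 and the table in Section 7.2 should instead say what the SDR contributes to PJI, and the protocol should acknowledge that uncoded antibiotic-only cases are not captured.
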